16.6 Analysis Plan

16.61 Local Recurrence Rate

All eligible patients who have undergone surgery that was not converted to a mastectomy and who did not have a finding of single contiguous area of malignancy on final pathology will be included in the analysis of the primary endpoint.

The cumulative incidence of local recurrences will be estimated in the competing risk framework as described by Marubini and Valsecchi where regional recurrences, distant recurrences and death without a local recurrence will be considered competing risks and contralateral breast and non-breast second primary cancers will not be considered competing risk. A 95 % Poisson confidence interval for the cumulative incidence of a local recurrence within 5 years will be constructed.

Gentilini *et al.* reported that cumulative incidence of local recurrence differed in terms of estrogen receptor status, HER2/neu expression, Nottingham grade, and Ki-67 expression (univariately) (Gentilini *et al.*, 2009). Gray's test will be used to explore whether the cumulative incidence of local recurrence differs with respect to these factors as well as progesterone receptor status, number of positive lymph nodes, number of foci, t-stage, age, perception of quality of life as measured by LASA at registration (poor: 0 to 3; middling: 4 to 7; good/excellent: 8 to 10), and fatigue as measured by LASA at registration (none to little: 0 to 3; some: 4 to 7; a great deal: 8 to 10).

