13.2 Conditions Requiring Study Termination

Patients who convert to a mastectomy for any reason within a year of initial surgery will go to the observation phase of the study. All data and forms prior to and up to mastectomy must be submitted. Tissue from the mastectomy should be submitted if possible. Patients will be followed for survival yearly for 5 years after treatment discontinuation.

Patients found to have any of the following:

- those with persistent positive margins who decline mastectomy;
- the dose constraint is not met (≤ 10 weeks of initial attempt of WBI planning in patients not receiving adjuvant chemotherapy, or ≤ 8 weeks after completion of chemotherapy for those patients receiving chemotherapy)

will have participation in the study terminated. The on-study material, surgery forms, pathology forms and the End of Active Treatment/Cancel Notification Form must be submitted. No further data submission is needed.

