16.2 Study Endpoints

The primary endpoint for this trial is the diagnosis of a local recurrence as a first event where a local recurrence is defined as histologic evidence of ductal carcinoma *in situ* or invasive breast cancer in the ipsilateral breast or chest wall.

The cumulative incidence of local recurrences will be estimated in the competing risk framework as described by Marubini and Valsecchi where regional recurrences, distant recurrences and death without a local recurrence will be considered competing risks and contralateral breast and non-breast second primary cancers will not be considered competing risk.

All eligible patients who have undergone breast conservation surgery with 2 or 3 sites of disease resected to negative margins (i.e., not converted to mastectomy or have not refused mastectomy for positive margins) will be included in the analysis of the primary endpoint.

Secondary clinical endpoints are:

- The conversion rate to mastectomy secondary to persistent positive margins; poor cosmesis within the first year of attempting breast conservation surgery (BCS); or inability to satisfy radiation dose constraints on the boost to the lumpectomy bed of each site of disease
- The type and severity of adverse effects of breast conserving surgery and radiation for women with multiple ipsilateral primary breast cancer (MIBC)
- The radiation-related side effects of whole breast radiation with a boost to 1 large or > 1 lumpectomy site
- The patient's perception of cosmesis.

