16.3 Sample Size Determination

Assuming a cohort of 200 eligible patients is enrolled over a 2 year period, the follow-up period after the close of enrollment is 5 years, and the number of local recurrences follows a Poisson distribution, the upper bounds of 95 % confidence interval for the cumulative incidence of a local recurrence within 5 years would fall below 8 % if at most 8 local recurrences occurred as a first event among these 200 patients.

It was originally planned to have an additional 30 patients enrolled to account for patients who withdraw consent prior to surgery, are found to be ineligible after signing a consent form, convert to mastectomy, or are found to have a single contiguous area of malignancy at final pathology. During the course of the study, it was found that many patients were being deemed ineligible after enrollment because the distance between lesions was outside the allowable range. This caused a high rate of ineligibilities. The protocol was amended and the ineligibility rate has subsequently decreased. However, in order to obtain the 200 evaluable patients needed for the primary endpoint, the study will need to enroll a total of 265 (35 additional) patients. Hence the target accrual for the study is 265 patients.

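### Sections 16.2 and 16.61 define different primary analysis sets: women who decline mastectomy for positive margins are out under one and in under the other, with no follow-up to record a recurrence

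*Combined protocol and SAP*

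**What the plan says.** The primary endpoint is local recurrence as a first event, and the protocol states its analysis set twice.

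- Section 16.2 restricts the set to eligible patients with 2 or 3 sites resected to negative margins. Its parenthesis explains this as "not converted to mastectomy or have not refused mastectomy for positive margins) will be included in the analysis of the primary endpoint".
- Section 16.61 takes "eligible patients who have undergone surgery that was not converted to a mastectomy and who did not have a finding of single contiguous area" (that is, one merged lesion at pathology). It has no margin condition and does not mention refusal of mastectomy.

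Section 16.3 plans on 200 eligible patients and enrols extra patients to cover losses. The reasons it lists are withdrawal of consent before surgery, ineligibility, conversion to mastectomy and a single contiguous lesion. Declining mastectomy is not listed.

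Section 13.2 terminates participation for "those with persistent positive margins who decline mastectomy" and for patients whose dose constraint is not met. The on-study, surgery, pathology and end-of-treatment forms are still due, and then "No further data submission is needed". Section 7.2 likewise sends women with persistent positive margins to mastectomy or off study.

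For the estimate, 16.61 names a competing-risk cumulative incidence. For the interval it names a 95% Poisson interval, without saying what count or exposure the events are divided by.

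**The concern.** A woman with persistent positive margins who declines mastectomy has had surgery and has not converted. If she met the entry criteria and her final pathology shows separate lesions, 16.61 read literally includes her and 16.2 excludes her. Her follow-up stops at termination, so under 16.61 she would be in the primary set with no means of recording the event being counted.

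Two things are at stake. First, the choice between the two sets is open and could be made after the results are known. Second, the success rule in 16.3 is a count among patients. If the Poisson interval uses the number of patients as its denominator, each decliner lowers the upper limit without being able to contribute an event.

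**Working it through.** **Inputs, all from 16.3.** The cohort is given as "Assuming a cohort of 200 eligible patients is enrolled over a 2 year period". The requirement is that the "upper bounds of 95 % confidence interval for the cumulative incidence of a local recurrence within 5 years would fall below 8" %, which is said to hold "if at most 8 local recurrences occurred as a first event among these 200 patients". The model is that "the number of local recurrences follows a Poisson distribution". The number of decliners, k, appears nowhere in the documents. It is an assumption, shown here from 0 to 20.

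**Step 1: reproduce the plan's cut-off.** The exact two-sided 95% Poisson upper limit for x events among n patients is U = χ²(0.975; 2(x+1)) / 2 / n.

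- x = 8: the limit on the count is 15.763; 15.763/200 = 7.88%, below 8%.
- x = 9: the limit on the count is 17.085; 17.085/200 = 8.54%, above 8%.

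The plan's figure of 8 is reproduced. The plan does not say whether the limit is one- or two-sided. A one-sided 95% limit would be 7.85% at 9 events and would allow 9, so two-sided is evidently meant.

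**Step 2: remove k decliners from a count of 200 that includes 8 recurrences.** The smallest passing n is 15.763/0.08 = 197.04, so at least 198 women are needed.

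| k | n = 200 − k | 8/n | Upper limit |
|---|---|---|---|
| 0 | 200 | 4.00% | 7.88% |
| 2 | 198 | 4.04% | 7.96% |
| 3 | 197 | 4.06% | 8.002% |
| 5 | 195 | 4.10% | 8.08% |
| 10 | 190 | 4.21% | 8.30% |
| 20 | 180 | 4.44% | 8.76% |

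With decliners counted in, the limit stays at 7.88%. At exactly 8 events, three of them separate a pass from a fail.

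**Step 3: other event counts.**

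- 7 events: the limit on the count is 14.42; 14.42/0.08 = 180.3, so n must be at least 181. About 20 of the 200 would have to be decliners before the result changed.
- 9 events: 17.085/0.08 = 213.6. At least 14 decliners would have to be added on top of 200 followed women for the criterion to be met (7.98% at n = 214).

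**Step 4: the estimator that 16.61 names.** Take an illustrative cohort of 200 − k followed women with 8 local recurrences between 0.7 and 4.8 years, 10 competing events between 0.9 and 4.9 years, and everyone else followed past 5 years. Add k decliners censored at 0.05 or 0.2 years. The 5-year cumulative incidence is the same with and without them: 4.06% for k = 3, 4.10% for k = 5, 4.21% for k = 10 and 4.44% for k = 20. They leave the risk set before the first event and so cannot dilute the estimate. Any dilution comes only from dividing by a patient count.

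**The case against.** The strongest reply is that 16.61 estimates recurrence by cumulative incidence, and step 4 shows that decliners do not dilute it. That stands. A reader might infer that the primary estimate is biased downward by a padded denominator, but the documents do not support that. Dilution is possible in the Poisson interval and in the 8-of-200 rule; it is not established, because 16.61 leaves the denominator open.

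Four further points carry weight.

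- A reader might infer that 13.2 stops all data on these women. It does not; only follow-up stops.
- A reader might infer that decliners will fill places among the 200. Section 16.3 does not list them as losses, but it speaks of patients evaluable for the primary endpoint, and 16.2 excludes them from that endpoint. The text does not settle it.
- The notes in 7.6 and 13.3 call patients who cannot or do not receive a boost ineligible. A decliner without a boost might leave both sets that way. However, 13.5 judges eligibility as at registration, so the passages conflict and this does not reliably close the gap.
- A reader might infer that 16.62 scores decliners as successful conservation. That endpoint is the conversion rate, and a woman who did not convert is correctly a non-conversion. Reporting decliners beside it is an option, not a correction.

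The three-patient result is also a boundary case, since it needs exactly 8 events and a raw-count denominator. None of these points removes the contradiction between the two definitions.

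**Conclusion.** The concern holds in a limited form. Sections 16.2 and 16.61 disagree about who is in the primary analysis. The 16.61 version, read literally, admits women whose later recurrences would not be collected.

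The numerical consequence is conditional. If the interval uses the raw patient count, and exactly 8 recurrences occur, and at least 3 of 200 counted women are decliners, the set chosen decides whether the upper limit falls below 8%. Away from that boundary a handful of decliners changes nothing. The cumulative incidence estimate is essentially unaffected, provided decliners are censored before the first recurrence. It would be natural to expect residual positive margins to carry a higher risk, but the documents give no figure for it, and no part of the calculation rests on it.

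The sets also differ on a second condition: 16.61 excludes a single contiguous lesion expressly, while 16.2 does not name it.

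**What to change.** State one primary set in the same words in 16.2, 16.3 and 16.61: eligible; 2 or 3 sites resected to negative margins as the protocol defines them; not converted to mastectomy; not declining mastectomy for persistent positive margins; and no single contiguous area on final pathology. The last condition must be kept, because 16.3 budgets for it.

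Then:

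- Say in 16.3 that decliners do not count toward the 200 evaluable patients.
- State the denominator or exposure of the Poisson interval, for example by tying it to the cumulative incidence estimate or to followed patients rather than to everyone enrolled.
- Say how the primary analysis treats patients terminated under 13.2 for an unmet dose constraint. They too have no follow-up, and changing the margin wording alone does not deal with them.
- Reconcile the boost notes in 7.6 and 13.3 with the definition of ineligibility in 13.5, so that eligible has one meaning in the analysis sets.
- Optionally, report the number who declined mastectomy with persistent positive margins beside the conversion rate in 16.62.

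The cost is wording, plus one optional count from forms that 13.2 already requires. The downside is a slightly smaller evaluable set. The changes should be made before the primary data are examined.

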16.5 Study Monitoring

16.51 Futility stopping rules

If more than 8 local recurrences are observed as a first event, the trial will stop as the 5 year local recurrence rate is unacceptably high.

A conversion to mastectomy rate of 25 % or more is considered to be unacceptably high. As such, consideration will be given to discontinuing

enrollment if 35 or more women among the first 100 women enrolled convert to mastectomy secondary to persistent positive margins or poor cosmesis within 6 months of BCS. The lower bound for 95 % binomial confidence interval for the conversion rate is 25.7 % (if 35 of 100 women convert to a mastectomy).

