(Compliance with Test Schedule Section 4.0)

	Surgery Phase	At completion of adjuvant chemotherapy (if applicable)	At completion of WBI	Observation post WBI follow-up
Patient Status: Treatment (Intervention)	X ¹			
Surgery	X ¹			
Contralateral Surgery	X ^{1,9}			
Pathology Information	X			
Adverse Event	X		X ^{4,7}	
Other Adverse Event	X		X ^{7,8}	
Patient Questionnaire: Active Monitoring	X ^{2,3}			X ^{2,3}
Surgeon Questionnaire: Active Monitoring	X ^{2,5}			
Patient Questionnaire: Booklet Compliance	X ¹			X ⁴
Blood Sample Submission: Institution	X ¹			
Tissue Sample Submission: Institution	X ¹			
Adjuvant Systemic Therapy Evaluation Form		X ⁶		
Radiation Treatment Plan Submission			X ⁷	
Radiation Therapy Information Form			X ⁷	
Start of Adjuvant Endocrine/ Biologic Therapy				X ¹⁷
Patient Status: Clinical Follow Up/Observation Evaluation/Observation				X ¹⁰
Termination of Endocrine Therapy				X ¹¹
Termination of Biologic Therapy				X ¹²
Off Treatment (Completion of WBI)			X	
NCCTG sites only:				
Notification – Grade 4 or 5 Non-AER Reportable Events/Hospitalization			At each occurrence (see Section 10.0)	
Notice of New Primary ¹³		At each occurrence	At each occurrence	At each occurrence
Recurrence Information ¹⁴		X	X	X
Local-Regional Recurrence		X	X	X
Documentation Submission ¹⁵				
Distant Recurrence		X	X	X
Documentation Submission ¹⁶				

Early Termination of Follow-Up

Consent Withdrawal

Lost to Follow-Up

These forms must be completed when the study participant is withdrawing consent for QOL (questionnaires), specimens, clinical follow-up only, or all follow-up or if they have become lost to follow-up. These forms are found in the Add Event dropdown list in Rave. Once added, they will be found in the Early Termination of Follow-Up Folder. **Please note:** If the study participant is refusing further study treatment, document the refusal by completing an Off Treatment Form, not a Consent Withdrawal Form.

1. Submit \leq 30 days following surgery.
2. Patient and surgeon questionnaire booklets must be ordered by the site from the CTSU using the form located on the CTSU website; the forms located in the appendices of the protocol can be downloaded and printed directly from the CTSU website for IRB submission only. Forms used by patients must be ordered from the CTSU.

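### The only worked form of the primary Poisson interval (8 events among 200) treats censored patients as event-free, unlike the cumulative incidence estimate it accompanies; and the year-7 analysis date no longer meets its own 5-year condition

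*Combined protocol and SAP*

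**What the plan says.** Section 16.61 sets the point estimate: "The cumulative incidence of local recurrences will be estimated in the competing risk framework", with regional recurrence, distant recurrence and death without local recurrence as competing risks. For precision it adds: "A 95 % Poisson confidence interval for the cumulative incidence of a local recurrence within 5 years will be constructed". It states no denominator, formula or rule for censored patients.

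The worked case is in 16.3. It assumes 200 eligible patients enrolled over 2 years, 5 years of follow-up after enrolment closes, and a Poisson count. The upper bound "would fall below 8 % if at most 8 local recurrences occurred as a first event among these 200 patients". Section 16.51 carries the same count with no denominator: "If more than 8 local recurrences are observed as a first event, the trial will stop".

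The primary population in 16.2 is "All eligible patients who have undergone breast conservation surgery with 2 or 3 sites of disease resected to negative margins". Section 18.2 provides forms for a participant who is "withdrawing consent for QOL (questionnaires), specimens, clinical follow-up only, or all follow-up or if they have become lost to follow-up". The documents give no expected rate of such losses. The extra enrolment in 16.3 is there to "account for patients who withdraw consent prior to surgery, are found to be ineligible after signing a consent form, convert to mastectomy", or to cover a single contiguous lesion at final pathology. Loss to follow-up after surgery is not on that list.

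On timing, 16.62 places the final analysis at year 7 and in the same sentence requires at least 5 years of follow-up. Section 16.4 gives about 25 months of accrual plus a further 5-6 months.

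**The concern.** The trial's conclusion is whether the upper limit for 5-year local recurrence lies below 8%. The estimate removes a patient from the risk set when she is censored. A count over 200 keeps her in the denominator as though she had been seen event-free to 5 years. With any censoring before 5 years the estimate exceeds events/200, but the upper limit does not move with it. The reported interval then belongs to a different and smaller quantity than the reported estimate, and the direction favours concluding that recurrence is below 8%.

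The analysis date bears on the same point: an analysis at month 84 with longer accrual adds administrative censoring that the worked case did not contemplate.

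**Working it through.** **Inputs.** From 16.3: N = 200, at most 8 events, threshold 8%, Poisson count. From 16.4: accrual of about 25 months plus 5-6, at 8-9 patients per month. From 16.62: year 7. Assumed, because the documents give no figure: constant loss of 0, 1 or 2% per year, competing events of 8% by 5 years, and uniform accrual.

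**1. Reproduce the plan's figure.** The exact two-sided 95% Poisson upper limit for d events is U(d) = chi-square(0.975; 2d+2)/2.
- U(8) = 15.763, and 15.763/200 = 7.88%, below 8%.
- U(9) = 17.085, and 17.085/200 = 8.54%, above 8%.

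So at most 8 of 200 is reproduced, and it is correct with complete follow-up. Competing events do not disturb it: without censoring the cumulative incidence is exactly d/N.

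**2. What censoring does.** Let F be the 5-year cumulative incidence estimate and define effective N = d/F. With complete follow-up this is 200; with censoring it is smaller. The limit that matches F is U(d)/(d/F). For 8 events it reaches 8% at 15.763/0.08 = 197.04. At an effective N of 197 the limit is 15.763/197 = 8.002%. The count form stays at 7.88% whatever the censoring.

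With constant loss r per year, effective N is about 200(1 - exp(-5r))/(5r):

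| Loss per year | Lost by year 5 | Effective N | Matched limit, 8 events | Count over 200 |
|---|---|---|---|---|
| 0% | 0% | 200 | 7.88% | 7.88% |
| 1% | 4.9% | 195.1 | 8.08% | 7.88% |
| 2% | 9.5% | 190.3 | 8.28% | 7.88% |

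The crossing at 197.04 corresponds to a loss of about 0.60% per year. With 7 events the matched limit stays below 8% down to 14.423/0.08 = 180.28, that is, an effective N of 181. Over this range of loss the split therefore concerns 8 events, which with 200 fully observed patients has probability 14.2% at a true 4% and 1.0% at a true 8%.

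**3. Error rate and power.** Exact, with no loss: P(X ≤ 8) for Binomial(200, 0.08) = 1.8%. Simulation with N = 200 and constant cause-specific hazards, for loss of 0/1/2% per year:

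| Chance of concluding below 8% | Count over 200 | Limit on effective N |
|---|---|---|
| True 8% (nominal 2.5%) | 1.8 / 2.3 / 2.7-2.8% | 1.8 / 1.2 / 1.3% |
| True 8%, analysis cut at year 7 | 2.0-2.1 / 2.5-2.6 / 3.1-3.2% | 1.7 / 1.3 / 1.4% |
| True 4% | 59 / 61 / 64% | 59 / 50 / 51% |

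Ranges show differences between simulation runs. Taking 4% or 12% competing events instead of 8% moves the figures without the cut by less than 0.6 points.

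**4. Year 7.** With 2 years of accrual, 24 + 60 = 84 months, which is year 7. With 25 + 5-6 = 30-31 months, 30 + 60 = 90 and 31 + 60 = 91 months, or year 7.5-7.6. As a cross-check, 265/9 = 29.4 and 265/8 = 33.1 months. At month 84 the last patient has 84 - 31 = 53 to 84 - 30 = 54 months (4.4-4.5 years). Patients enrolled after month 24 fall short: 1 - 24/30 = 20% to 1 - 24/31 = 23%.

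**The case against.** The strongest reply is that the plan is less open than the missing formula suggests. Sections 16.3 and 16.51 together point to exact Poisson limits over the number evaluable. That stands. A reader might infer that the form is undetermined and could be picked after the data are seen; the documents do not support this, because the worked case and the stopping rule both lean to the count form. The criticism is that this form does not match the estimator under censoring.

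Second, the size rests on assumptions. No loss rate is given, and the analysed N need not be exactly 200. With 205 evaluable patients at 1% yearly loss, or 210 at 2%, 8 events give a matched limit of 7.88% or 7.89% and still pass. This also stands.

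Third, follow-up is better protected than the forms in 18.2 suggest. Section 13.3 keeps patients who refuse or stop WBI under observation for 5 years, and 13.4 moves patients who refuse study tests or procedures to yearly disease and vital-status monitoring. Some uses of the 18.2 form, such as withdrawal from questionnaires only, do not censor recurrence. This limits the amount of censoring but does not remove it.

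Fourth, a reader might infer that dose-constraint terminations under 13.2, where "No further data submission is needed", form a large unplanned loss. The documents do not support that. Sections 7.62 and 7.63 recommend mastectomy for these patients, and 7.6 calls those who cannot or do not receive a boost ineligible. Both reasons are in the 16.3 list, so only a residual subgroup is unclear.

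Finally, the 5-year condition in 16.62 could be read as governing over year 7, whose origin is not stated. That is possible, but the sentence should not need the choice.

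**Conclusion.** The point holds as a mismatch of modest size. The only worked interval is exact under complete 5-year follow-up and too low for its accompanying estimate under the withdrawal and loss that 18.2 foresees. For assumed losses up to 2% per year and N = 200, the false below-8% rate rises from 1.8% to about 2.7-2.8%, or about 3.1-3.2% with a year-7 cut, against 2.5%. At 1% loss without the cut it stays within nominal. The decision changes only near the boundary, in practice at 8 events.

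Two stronger readings should be resisted. The 8-of-200 figure is not wrong: it is reproduced, and it holds with complete data. Nor is the error rate badly inflated: the excess is a fraction of a percentage point and depends on loss rates that the documents do not give.

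The year-7 conflict is separate and is a matter of consistency. If year 7 runs from first registration and accrual is uniform, about 20-23% of patients lack 5 years at month 84. It is not needed for error control once the interval allows for censoring.

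**What to change.** 1. **Section 16.61.** Specify one interval: exact Poisson 95% limits for the number of local recurrences within 5 years, divided by effective N, where effective N is that number divided by the 5-year cumulative incidence estimate F (or the number evaluable if there are no events). State that 8% is excluded if the upper limit is below 8%, and name the time origin.
2. **Section 16.3.** Say that 8 of 200 assumes complete 5-year follow-up, and update the 2-year accrual.
3. **Section 16.62.** Replace year 7 with the date on which the last evaluable patient reaches 5 years of follow-up from the named origin.

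**Cost.** The first change needs only wording and standard software, and it leaves the 8-of-200 rule unchanged with complete follow-up. Its real price is power: at a true 4% and an assumed 1-2% yearly loss, the chance of concluding below 8% is about 50-51%, against 61-64% if lost patients count as event-free. The limit on effective N is also conservative, with a false below-8% rate of about 1.2-1.3% at those losses. The timing change moves the final analysis to about year 7.5-7.6 from first registration, and later if the origin is the end of WBI.
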